10.3.4 Reporting of Serious Adverse Event and Adverse Event of Special Interest

SAE and AESI Reporting via Electronic Data Collection Tool

The primary mechanism for reporting an SAE/AESI will be the electronic data collection tool. If the electronic system is unavailable, then the site will use the paper SAE/AESI data collection tool (see next table) to report the event within 24 hours.

The site will enter the SAE/AESI data into the electronic system as soon as it becomes available.

When calling to report an SAE/AESI, state that you are reporting an SAE/AESI and give the Investigator's name, your name, the telephone number where you can be reached, and the protocol number and title.

The Investigator and the Sponsor (or Sponsor's designated agent) will review each SAE/AESI report and the Sponsor/██████████ will evaluate the seriousness and the causal relationship of the event to study intervention. In addition, the Sponsor (or Sponsor's designated agent) will evaluate the expectedness according to the Reference Safety Information (Investigator Brochure or Summary of Product Characteristics). Based on the Investigator and Sponsor's assessment of the event, a decision will be made concerning the need for further action.

After the study is completed at a given site, the electronic data collection tool will be taken offline to prevent the entry of new data or changes to existing data.

If a site receives a report of a new SAE/AESI from a study patient or receives updated data on a previously reported SAE/AESI after the electronic data collection tool has been taken offline, then the site can report this information on a paper SAE/AESI form (see next table) or by telephone.

Contacts for SAE/AESI reporting can be found below.

SAE Reporting via Paper Data Collection Tool

Email or facsimile transmission of the SAE/AESI paper data collection tool is the preferred method to transmit this information.

In rare circumstances and in the absence of email/facsimile equipment, notification by telephone is acceptable with a copy of the SAE/AESI paper data collection tool sent by overnight mail or courier service.

Initial notification via telephone does not replace the need for the Investigator to complete and sign the SAE/AESI data collection tool within the designated reporting timeframes.

Contacts for SAE/AESI reporting can be found below.

Suspected Unexpected Serious Adverse Reactions (SUSARs)

Any AE that is serious, associated with the use of the study intervention, and unexpected (SUSAR) has additional reporting requirements, as described below.

If the SUSAR is fatal or life-threatening, associated with study intervention, and unexpected, regulatory authorities and IECs will be notified within seven calendar days after the Sponsor

learns of the event. Additional follow-up (cause of death, autopsy report, and hospital report) information should be reported within an additional 8 days (15 days total).

If the SUSAR is not fatal or life-threatening but is otherwise serious, associated with study intervention, and unexpected, regulatory authorities and IECs will be notified within 15 calendar days after the Sponsor learns of the event.

The Sponsor will notify the Investigators in a timely fashion of relevant information about SUSARs that could adversely affect the safety of patients. Follow-up information may be submitted if necessary.

The Sponsor will also provide annual safety updates to the regulatory authorities and IECs responsible for the study. These updates will include information on SUSARs and other relevant safety findings.

AE=adverse event; IEC=Institutional Review Board; SAE=serious adverse event; SUSAR=suspected unexpected serious adverse reactions

Serious Adverse Events Contact Details

SERIOUS ADVERSE EVENT REPORTING INSTRUCTIONS

(See SAE Reporting Instructions)

1. Telephone the [REDACTED] to inform him/her that you are emailing/faxing a SAE form. If the [REDACTED] is not available or you are calling after business hours (8:30 am to 5:30 pm Eastern time, Monday to Friday), leave a message in their voice mailbox.
2. Provide the [REDACTED] with the Principal Investigator's name, your name, the telephone number where you can be reached, and the protocol number and title.
3. Email/Fax the SAE form and any supporting documentation to the [REDACTED] within 24 hours of becoming aware of the event.
4. After business hours, the [REDACTED] may be reached through [REDACTED] 24-hour answering service at [REDACTED]. Give the answering service the protocol number, the study intervention name, and the Sponsoring pharmaceutical company.

10.4 Appendix 4: Contraceptive and Barrier Guidance

10.4.1 Definitions

Women of Childbearing Potential (WOCBP)

A woman is considered fertile following menarche and until becoming post-menopausal unless permanently sterile (see below).

Women in the following categories are not considered to be a woman of childbearing potential:

1. Premenarchal
2. Premenopausal female with one of the following:
 - Documented hysterectomy
 - Documented bilateral salpingectomy
 - Documented tubal ligation
 - Documented bilateral oophorectomy
3. Post-menopausal female
 - A post-menopausal state is defined as no menses for 12 months without an alternative medical cause. A high FSH level in the post-menopausal range (> 40 U/mL) may be used to confirm a post-menopausal state in women not using hormonal contraception or hormonal replacement therapy (HRT). However, in the absence of 12 months of amenorrhea, a single FSH measurement is insufficient.

10.4.2 Contraception Guidance

Male patients

Male patients with female partners of childbearing potential (including partners who are pregnant or breastfeeding [including pumping breast milk to feed to a child]) must use contraception if any of the following criteria are met:

- Genotoxic study medication
- Study medication where reproductive toxicology studies have not yet been conducted

- Study medication with demonstrated or suspected human teratogenicity/fetotoxicity at subtherapeutic exposure levels if relevant systemic concentrations may be achieved in WOCBP from exposure to seminal fluid

Male patients with female partners of childbearing potential are eligible to participate if they agree to ONE of the following during the protocol-defined time frame:

- Are abstinent from penile-vaginal intercourse as their usual and preferred lifestyle (abstinent on a long term and persistent basis) and agree to remain abstinent.
- Agree to use a male condom plus partner use of a contraceptive method with a failure rate of < 1% per year as described in the table below when having penile-vaginal intercourse with a WOCBP who is not currently pregnant.
- Agree to use a male condom when having penile-vaginal intercourse WOCBP who is currently pregnant.

In addition, male patients must refrain from donating sperm for the duration of the study and for 3 months after the final dose of study medication.

Male patients with a pregnant or breastfeeding (including pumping breast milk to feed to a child) partner must agree to remain abstinent from penile vaginal intercourse or use a male condom during each episode of penile penetration during the study and for at least 3 months after the final dose of study medication.

Female patients

Female patients of childbearing potential are eligible to participate if they agree to use a highly effective method of contraception consistently and correctly as described in the table below. If the Investigator has another method not listed below but is proven to have a failure rate < 1%, then this method may be considered after discussion with the Medical Monitor or Sponsor study physician.

Highly Effective Contraceptive Methods

Highly Effective Contraceptive Methods That Are User Dependent

- Failure rate of < 1% per year when used consistently and correctly.
- Combined (estrogen and progestogen containing) hormonal contraception associated with inhibition of ovulation
 - Oral

- Intravaginal
 - Transdermal
- Progestogen only hormonal contraception associated with inhibition of ovulation
 - Oral
 - Injectable

Highly Effective Methods That Are User Independent

- Implantable progestogen only hormonal contraception associated with inhibition of ovulation:
 - Intrauterine device (IUD)
 - Intrauterine hormone-releasing system (IUS)
 - Bilateral tubal occlusion

Vasectomized partner

A vasectomized partner is a highly effective contraception method provided that the partner is the sole male sexual partner of the WOCBP and the absence of sperm has been confirmed. If not, an additional highly effective method of contraception should be used.

Sexual abstinence

Sexual abstinence is considered a highly effective method only if defined as refraining from heterosexual intercourse during the entire period of risk associated with the study medication. The reliability of sexual abstinence needs to be evaluated in relation to the duration of the study and the preferred and usual lifestyle of the patient.

- Women of childbearing potential should only be included after a confirmed menstrual period and a negative highly sensitive serum pregnancy test.
- Additional urine pregnancy testing should be performed at monthly intervals during the treatment period and at End of Treatment/End of Study, after the final dose of study medication and as required locally.
- Pregnancy testing will be performed when pregnancy is suspected
- Pregnancy testing will be performed at Screening and at every post-Screening visit before study medication application.
- If a study patient is pregnant and stays in the study for observation no pregnancy testing will be performed as long as the pregnancy lasts.

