8.4.5 Pregnancy

Details of all pregnancies in female patients and, if indicated, partners of male patients will be collected after the start of study intervention and until time period for reporting pregnancies should align with the time period for post-intervention contraception determined in Section 5.1.

If a pregnancy is reported, the Investigator will record pregnancy information on the appropriate form and submit it to the Sponsor within 24 hours of learning of the female patients or partner of male patient (after obtaining the necessary signed informed consent from the partner) pregnancy and should follow the procedures outlined in [Appendix 4](#) (Section 10.4).

While pregnancy itself is not considered to be an AE or SAE, any pregnancy complication or elective termination of a pregnancy for medical reasons will be reported as an AE or SAE.

Abnormal pregnancy outcomes (e.g., spontaneous abortion, fetal death, stillbirth, congenital anomalies, ectopic pregnancy) are considered to be SAEs and will be reported as such.

The patient/pregnant partner will be followed to determine the outcome of the pregnancy. The Investigator will collect follow-up information on the patient/pregnant partner and the neonate and the information will be forwarded to the Sponsor.

Any post-study pregnancy-related SAE considered reasonably related to the study intervention by the Investigator will be reported to the Sponsor as described in Section 8.4.4. While the Investigator is not obligated to actively seek this information in former study patients/pregnant partners, he or she may learn of an SAE through spontaneous reporting.

Any female patient who becomes pregnant while participating in the study will discontinue study intervention or be withdrawn from the study.

Prior to continuation of study intervention following pregnancy, the following must occur:

- a. The Sponsor and the relevant IRB give written approval.
- b. The patient gives signed informed consent.
- c. The Investigator agrees to monitor the outcome of the pregnancy and the status of the patient and her offspring.

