10.4.2.1 Collection of Pregnancy Information

Male Patients with Female Partners Who Become Pregnant

- The Investigator will attempt to collect pregnancy information on any male patient's female partner who becomes pregnant while the male patient is in this study. This applies only to male patients who receive the study drug. If the study patient is later found to be on placebo, then pregnancy data collection can stop.
- After obtaining the necessary signed informed consent from the pregnant female partner directly, the Investigator will record pregnancy information on the appropriate form and submit it to the Sponsor within 24 hours of learning of the partner's pregnancy. The female partner will also be followed to determine the outcome of the pregnancy. Information on the status of the mother and child will be forwarded to the Sponsor. Generally, the follow-up will not be required after birth of the child or elective termination of pregnancy. Any termination of the pregnancy will be reported regardless of fetal status (presence or absence of anomalies) or indication for the procedure.

Female Patients Who Become Pregnant

- The Investigator will collect pregnancy information on any female patient who becomes pregnant while participating in this study. This applies only to female patients who receive the study drug. If the study patient is later found to be on placebo, then pregnancy data collection can stop. Information will be recorded on the appropriate form and submitted to the Sponsor within 24 hours of learning of a patient's pregnancy. The patient will be followed to determine the outcome of the pregnancy. The Investigator will collect any follow-up information on the patient and the neonate, and the information will be forwarded to the Sponsor. Generally, follow-up will not be required after birth of the child or elective termination of pregnancy. Any termination of the pregnancy will be reported, regardless of fetal state (presence or absence of anomalies) or indication for the procedure.

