- While pregnancy itself is not considered to be an AE or SAE, any pregnancy complication or elective termination of a pregnancy will be reported as an AE or SAE. A spontaneous abortion is always considered to be an SAE and will be reported as such. Any post-study pregnancy-related SAE considered reasonably related to study drugs by the Investigator will be reported to the Sponsor as described in Section 8.4.4. While the Investigator is not obligated to actively seek this information in former study patients, he or she may learn of an SAE through spontaneous reporting.
- Any female patient who becomes pregnant while participating in the study will discontinue the study drugs and will be withdrawn from the study.

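### The protocol gives two answers on dosing after a pregnancy (8.4.5 against 10.4.2.1), and Appendix 4 sets an entry condition that nothing else in the plan schedules

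*Protocol*

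**What the plan says.** **Hazard and benefit.** Protocol 2.2.1 reports teratogenicity in rats and rabbits and embryo loss in rabbits, and 8.4.6 makes embryo-fetal toxicity an event of special interest. Protocol 2.3.2 expects no benefit to patients from 7 days of treatment.

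**Pregnancy on study.** Protocol 8.4.5 says that a female patient who becomes pregnant "will discontinue study intervention or be withdrawn from the study". It then goes on: "Prior to continuation of study intervention following pregnancy, the following must occur". Three items follow: (a) "The Sponsor and the relevant IRB give written approval"; (b) the patient signs consent; (c) "The Investigator agrees to monitor the outcome of the pregnancy and the status of the patient and her offspring". Section 10.4.2.1 belongs to the Appendix 4 to which 8.4.5 sends the Investigator. It says that she "will discontinue the study drugs and will be withdrawn from the study". Its only exception concerns data, not dosing: "If the study patient is later found to be on placebo, then pregnancy data collection can stop".

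**Testing.** Appendix 4 (10.4.2) gives the entry condition "Women of childbearing potential should only be included after a confirmed menstrual period and a negative highly sensitive serum pregnancy test" and adds: "Pregnancy testing will be performed at Screening and at every post-Screening visit before study medication application". The rest of the plan names a urine test only. This holds for exclusion 1 (5.2), 8.2.5, 8.3.6, the schedule (Table 1-1) and Table 10-1, and for the SAP copies in 6.1 and 6.3. Reproductive history is collected (8.2.3), but no confirmed-period condition appears outside Appendix 4.

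**The concern.** For a compound with these animal findings, the pregnancy instructions should have one meaning.

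On dosing, one section opens a route that the other closes. Since 8.4.5 itself points to Appendix 4, neither section plainly overrides the other.

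On entry, a woman can pass exclusion 1 and every scheduled check without meeting the Appendix 4 condition. The protocol bars waivers (Sections 5 and 8) and says it must be followed to the letter (10.1.11). A site that works from the schedule therefore departs from a written condition without being told how to meet it. SAP 4.4.3.1 says that deviations from entry criteria will be described, and the protocol does not settle whether a missing serum test is one.

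**Working it through.** No sizing or error-rate calculation applies. The check compares current text and counts scheduled tests.

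**1. What the continuation clause covers.** Dosing lasts 7 days within about 42 days of participation (4.1, 4.3), and there is no treatment after the study (6.6). Restarting after delivery is therefore not possible. Item (c) has the pregnancy outcome still to come. The clause can only mean dosing during a known pregnancy.

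**2. The stop rules side by side.**

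| Place | Study drug | Participation |
|---|---|---|
| 8.4.5, stop sentence | stop, or be withdrawn | either |
| 8.4.5, items (a) to (c) | may continue if all three are met | stays in |
| 10.4.2.1 | stop, no exception | withdrawn |
| 10.4.2, observation bullet | not stated | may stay for observation |
| 7.1 | stopped | stays for safety monitoring |

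Row 2 contradicts row 3 on drug. Row 3 also differs from rows 4 and 5 on staying in the study.

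**3. The entry test.** Urine only: 5 protocol places (exclusion 1, 8.2.5, 8.3.6, Table 1-1, Table 10-1) and 2 SAP copies (6.1, 6.3). Serum plus a confirmed menstrual period: 1 place (10.4.2). Scheduled serum tests: 0. These counts show where edits are needed; they do not measure harm.

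**4. Timing.** A patient who completes has 3 scheduled tests: Screening, Day -1 and Day 14.
- There is no Day 0 (SAP 4.2.2), so Day -1 to Day 14 is 1 + 13 = 14 days.
- No test is scheduled between those two days, and all 7 dosing days fall there.
- Day 14 comes 14 − 7 = 7 days after the last dose.

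A pregnancy would thus be found during dosing only by an unscheduled test, for example on suspicion (10.4.2).

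**5. The bullet on every later visit.** The answer depends on what a visit is.
- If each dosing day is a visit (the synopsis speaks of visits on Days -1 to 10), 7 pre-dose tests are required on Days 1 to 7 and 0 are scheduled, so 7 − 0 = 7 are missing.
- If the in-house stay is one visit (SAP Figure 3-2 numbers three visits in all), the Day -1 test meets the bullet and 0 are missing.

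**The case against.** The strongest reply is that little can happen in practice. Section 8.4.5 opens with a stop rule. The continuation clause needs Sponsor approval, IRB approval and signed consent, all obtained before the last of seven in-house doses, after an unscheduled test. Women of childbearing potential must use highly effective contraception from consent (inclusion 5b). This stands. A reader might infer that a site could keep dosing a pregnant patient on its own authority; item (a) rules that out. The two sections still disagree, and the protocol gives no reason for the route.

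On entry, a reader might infer that the serum and urine rules are incompatible. They are not: a site can do both, and Appendix 2 allows additional tests. Sites also have a working urine rule, because Appendix 2 refers to Section 5 for eligibility and Section 8 requires adherence to the schedule. What remains is that nothing tells a site to do the serum test or the menstrual-period check. Treating the Appendix 4 sentence as soft guidance does not help much, since 8.3.6 states its urine condition with the same kind of wording. That Appendix 4 looks like template text (it asks for monthly tests in a 7-day study) explains the mismatch but does not remove it.

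A reader might also infer that seven pre-dose tests are missing, or that urine-based entry protects less well. The first depends on an undefined term. For the second, the documents give no data on how serum and urine tests perform.

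**Conclusion.** The point holds as a minor to moderate alignment of safety text.

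- **Dosing:** 8.4.5 and 10.4.2.1 contradict each other, and 8.4.5 provides for dosing in an ongoing pregnancy. Practical exposure is small: three conditions and a window of at most 7 dosing days.
- **Entry:** one written condition for women of childbearing potential has no scheduled procedure behind it. The two rules are compatible; the gap is that only one is put into effect.
- **Pre-dose testing:** a conflict of 7 tests or none, depending on what counts as a visit. It is not established as a conflict.

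No loss of protection is quantified, and the statistical analysis is unaffected. The first conclusion rests on reading item (c) as describing a continuing pregnancy, which the study's length supports.

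**What to change.** **Dosing.** Delete the continuation sentence and items (a) to (c) from 8.4.5. In both 8.4.5 and 10.4.2.1, state that study drug is stopped permanently and the patient is followed to pregnancy outcome. Keep the placebo exception in 10.4.2.1. Safety follow-up after stopping then follows 7.1 unless the patient withdraws.

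**Entry test.** Choose one rule, for women of childbearing potential only.
- *Urine:* align Appendix 4 to the urine tests at Screening and Day -1.
- *Serum:* add the serum test and menstrual-period check at Screening through inclusion 5b, 8.2.5, 8.3.6, the schedule and Table 10-1, with SAP 6.1 and 6.3. Do not use exclusion 1. It covers all female patients, so a menstrual-period condition there would shut out the post-menopausal and hysterectomised women whom inclusion 5a admits.

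Under either option, state that the Day -1 test satisfies the pre-dose bullet, and remove the monthly wording.

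**Cost.** A protocol amendment with IRB approval (10.1.1) and possibly a consent form revision (10.1.3). The urine option adds no procedure. The serum option adds one serum test and one history check per woman of childbearing potential.

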10.4.2.1 Collection of Pregnancy Information

Male Patients with Female Partners Who Become Pregnant

- The Investigator will attempt to collect pregnancy information on any male patient's female partner who becomes pregnant while the male patient is in this study. This applies only to male patients who receive the study drug. If the study patient is later found to be on placebo, then pregnancy data collection can stop.
- After obtaining the necessary signed informed consent from the pregnant female partner directly, the Investigator will record pregnancy information on the appropriate form and submit it to the Sponsor within 24 hours of learning of the partner's pregnancy. The female partner will also be followed to determine the outcome of the pregnancy. Information on the status of the mother and child will be forwarded to the Sponsor. Generally, the follow-up will not be required after birth of the child or elective termination of pregnancy. Any termination of the pregnancy will be reported regardless of fetal status (presence or absence of anomalies) or indication for the procedure.

Female Patients Who Become Pregnant

- The Investigator will collect pregnancy information on any female patient who becomes pregnant while participating in this study. This applies only to female patients who receive the study drug. If the study patient is later found to be on placebo, then pregnancy data collection can stop. Information will be recorded on the appropriate form and submitted to the Sponsor within 24 hours of learning of a patient's pregnancy. The patient will be followed to determine the outcome of the pregnancy. The Investigator will collect any follow-up information on the patient and the neonate, and the information will be forwarded to the Sponsor. Generally, follow-up will not be required after birth of the child or elective termination of pregnancy. Any termination of the pregnancy will be reported, regardless of fetal state (presence or absence of anomalies) or indication for the procedure.
- While pregnancy itself is not considered to be an AE or SAE, any pregnancy complication or elective termination of a pregnancy will be reported as an AE or SAE. A spontaneous abortion is always considered to be an SAE and will be reported as such. Any post-study pregnancy-related SAE considered reasonably related to study drugs by the Investigator will be reported to the Sponsor as described in Section 8.4.4. While the Investigator is not obligated to actively seek this information in former study patients, he or she may learn of an SAE through spontaneous reporting.
- Any female patient who becomes pregnant while participating in the study will discontinue the study drugs and will be withdrawn from the study.

